7.3.4. End of Treatment Visit

Subjects should return to the study site for an End of Treatment Visit within approximately 7 days after treatment discontinuation of all study medication (CPI 613[®] + mFFX or FFX) and prior to initiation of subsequent anticancer therapy. Adverse events and concomitant medications will be reviewed at this visit, and the following assessments should be completed:

- Physical Examinations
- Vital Signs
- ECOG Performance Status
- Obtain CT scan (or MRI) if radiologic disease progression was not documented in the previous CT scan (or MRI) unless the latter one was performed within the last 14 days
- Blood sample collection for the following tests: Hematology, Blood Chemistry, and CA 19-9

- Collect AE and SAE
- Pregnancy test
- NCCN-FACT FHSI-18 Questionnaire

7.3.5. Long-Term Follow-up

After the End of Treatment visit, subjects will enter long-term follow-up during which information on the subject’s survival status, disease progression and subsequent anticancer therapy will be obtained by the site every 2 months according to the protocol with a time window of +/- 7 days. Information may be collected by chart review, phone calls, clinic visits, or other means as appropriate. Long-term follow-up will continue until the subject dies, is lost to follow up, or withdraws consent.

Follow up for OS:

OS will be monitored every 2 months via telephone contact, review of hospital records, death records, social media, etc. as allowed by local laws after treatment termination (Note: During every post-study treatment telephone contact, information related to cancer treatment received will also be collected). OS and PFS will be calculated from the day of randomization.

7.3.6. Schedule of Events Table

Table 16 Schedule of Events: Experimental Arm

Experimental Arm: devimistat + mFFX								
Assessments	Pre-Study Screen	Cycle 1 (+/- 24 hr.) and Subsequent Cycles (+/- 24 hr.)					End of treatment	Follow-Up Every 2 Months Until Death
		Day 1	Day 2	Day 3	Day 4	Days 5-14		
Informed consent	√							
Medical history	√							
Pregnancy test for women of childbearing Potential (monthly- day 1 of even numbered cycle)	√	√					√	
Hemoglobin A1c (HbA1c)	√							
devimistat administration (dosing)		√		√				

A Phase III Multi-Center Open-Label Randomized Trial to Evaluate Efficacy and Safety of FOLFIRINOX (FFX) versus Combination of CPI-613 with modified FOLFIRINOX (mFFX) in Patients with Metastatic Adenocarcinoma of the Pancreas

Protocol: PANC003

Version 9.0

June 10, 2021

mFOLFIRINOX (mFFX)		√	√	√				
AE and Con. Med. Assessment		AEs and con meds will be assessed at each patient visit						
Myeloid growth factor (as per institutional guidelines)*					√			
Evaluation of symptoms and vital signs ⁷	√	√					√	
ECOG performance status ⁶ and survival	√	√					√	
Clinical chemistry, hematology and coagulation	√	√				√ (day 7 or 8)	√	
Triphase contrast CT of the chest, abdomen and pelvis (or MRI if needed) (every 8 weeks)	√						√ (unless one was performed within the last 14 days)	
Blood sampling for biomarker ¹	√							
CA19-9 (every 8 weeks up to 12 cycles and every 4 weeks beyond 12 cycles)	√	√					√	
Blood sampling for Full PK Analysis ²		√		√				
Blood sampling for Sparse PK Analysis ³		√		√				
Cardiac Marker (Troponin I) ⁸		√		√				
Full ECG ⁴		√		√				
Sparse ECG ⁵		√		√				
Phone contact								√
NCCN-FACT FHSI-18 Questionnaire ⁶	√	√					√	

*Myeloid growth factor can be given at Day 4 or any day at the discretion of the treating physician per ASCO and institutional guidelines

¹ Prior to treatment initiation (within 4 weeks prior to 1st dose) and prior to each restaging scan.

² Full PK analysis will be carried out only for cycle 1. For Full PK sampling schedule see Section 7.1.1, Table 12

³ see Sparse PK sampling schedule in Section 7.1.1, Table 13

⁴ Full ECG measurement will be carried out only for cycle 1. For Full ECG measurement schedule see Section 7.1.1, Table 14

⁵ see Sparse ECG measurement schedule in Section 7.1.1, Table 15

⁶ at baseline and day 1 of every even numbered cycle

⁷ Vital signs include heart rate

⁸ see Cardiac Marker (Troponin I) schedule under Section 7

Table 17 Schedule of Events: Control Arm

Control Arm 2: FFX								
Assessments	Pre- Study Screen	Cycle 1 (+/- 24 hr.) and Subsequent Cycles (+/- 24 hr.)					End of Treatment	Follow-Up Every 2 Months Until Death
		Day 1	Day 2	Day 3	Day 4	Days 5-14		
Informed consent	√							
Medical history	√							
Pregnancy test for women of childbearing potential (monthly- day 1 of even numbered cycle)	√	√					√	
Hemoglobin A1c (HbA1c)	√							
FOLFIRINOX (FFX)		√	√	√				
AE and Con. Med. Assessment		AEs and con. meds will be assessed at each patient visit						
Myeloid growth factor (as per institutional guidelines)*					√			
Evaluation of symptoms and vital signs ⁶	√	√					√	
ECOG performance status ⁵ and survival	√	√					√	
Clinical chemistry, hematology and coagulation	√	√				√ (day 7 or 8)	√	
Triphase contrast CT of the chest, abdomen and pelvis (or MRI if needed) ¹	√						√ (unless one was performed within the last 14 days)	
Blood sampling for biomarker ²	√							
Cardiac Marker (Troponin I) ⁴		√		√				
CA19-9 every 8 weeks up to 12 cycles and every 4 weeks beyond 12 cycles)	√	√					√	
Sparse ECG ³		√		√				
Phone contact								√
NCCN-FACT FHSI-18 Questionnaire ⁵	√	√					√	

* Myeloid growth factor can be given at day 4 or any day at the discretion of the treating physician per ASCO and institutional guidelines

¹ restaging scans will be performed every 8 weeks +/-7 days

² Prior to treatment initiation (within 4 weeks prior to 1st dose) and prior to each restaging scan.

³ see Sparse ECG measurement schedule in Section 7.1.1, Table 15

⁴ see Cardiac Marker (Troponin I) schedule under Section 7

⁵ at baseline and day 1 of every even numbered cycle

⁶ Vital signs include heart rate

7.4. Concomitant Medications, Treatments, and Procedures

All concomitant prescription medications taken during study participation will be recorded on the case report forms (CRFs) such as prescription medications, over the counter medication, non-prescription medications. Concomitant use of anti-emetics is permitted for patients with disease-related nausea. Concomitant medicines that prolong QTc such as those listed in the table below can be taken after patient enrollment/baseline visit (C1D1) at the discretion of treating physician to manage an emergent condition. If the treating physician determines there is a need for other medications that are not listed below, it should be discussed with trial medical monitor.

Cardiac drugs	
 • Atenolol • Digoxin • Diltiazem • Enoxacin • Flecainide • Propafenone • Quinidine
Anti-depressants	
 • Amitriptyline • Doxepin • Fluoxetine • Imipramine • Nortriptyline • Paroxetine
Antipsychotics	
 • Aripiprazole • Clozapine • Haloperidol • Risperidone • Thioridazine
Antihistamines	
 • Lorazepam • Diphenhydramine • Hydroxyzine
Antimicrobials	
 • Cefepime • Ceftriaxone • Levofloxacin • Meropenem • Piperacillin-tazobactam • Vancomycin
Other drugs	
 • Fentanyl • Gabapentin • Lidocaine • Morphine • Oxycodone

© 2021, Rafael Pharmaceuticals, Inc. All rights reserved. This document is confidential and proprietary to Rafael Pharmaceuticals, Inc.

7.5. Prophylactic Medications, Treatments, and Procedures

All supportive measures are at the discretion of the treating physician. Supportive treatment as co-medications may include anti-emetic, anti-diarrhea, anti-pyretic, anti-allergic, anti-hypertensive medications, analgesics, antibiotics, allopurinol, and others such as blood products and bone marrow growth factors. Patients may use erythropoietin for chronic anemia. The treating physician may utilize erythropoietic factors, or blood or platelet transfusions at their discretion in addition to protocol mandated dose adjustments (see Section 6.1.6.2). The use of co-medications will be documented through treatment for individual patients.

7.6. Participant Access to Study Agent at Study Closure

Rafael Pharmaceuticals will make every attempt to ensure patients randomized to the study arm who are deriving clinical benefit will continue to have access to devimistat following study closure.

8.1. Specification of Safety Parameters

8.1.1. Definition of Adverse Events (AE)

An adverse event (AE) is defined as any undesired medical occurrence in a patient receiving a study treatment and which does not necessarily have a causal relationship with this treatment. An AE can therefore be any unfavorable sign (including an abnormal laboratory finding), symptom, or disease temporarily associated with the study treatment, whether or not related to the study drug.

8.1.2. Definition of Serious Adverse Events (SAE)

An AE or suspected adverse reaction is considered "serious" if, in the view of either the investigator or sponsor, it results in any of the following outcomes:

- Results in death
- Is life-threatening
- Requires hospitalization (initial or prolonged)
- Results in persistent or significant disability/ incapacity
- Is a congenital anomaly/birth defect
- Is otherwise considered as medically important

Important medical events that may not result in death, be life-threatening, or require hospitalization may be considered serious when, based upon appropriate medical judgment, they may jeopardize the patient or subject and may require medical or surgical intervention to prevent one of the outcomes listed in this definition. Examples of such medical events include allergic bronchospasm requiring intensive treatment in an emergency room or at home, blood dyscrasias or convulsions that do not result in inpatient hospitalization, or the development of drug dependency or drug abuse.

Events not to be considered as AEs/SAEs

Medical conditions present at the initial trial visit that do not worsen in severity or frequency

during the trial are defined as baseline medical conditions and NOT to be considered AEs.

8.1.3. Definition of Unanticipated Problems (UP)

OHRP considers unanticipated problems involving risks to participants or others to include, in general, any incident, experience, or outcome that meets all of the following criteria:

1. Unexpected in terms of nature, severity, or frequency given (a) the research procedures that are described in the protocol-related documents, such as the IRB-approved research protocol and informed consent document; and (b) the characteristics of the participant population being studied;
2. Related or possibly related to participation in the research (“possibly related” means there is a reasonable possibility that the incident, experience, or outcome may have been caused by the procedures involved in the research); and
3. Suggests that the research places participants or others at a greater risk of harm (including physical, psychological, economic, or social harm) than was previously known or recognized.

This study will use the OHRP definition of UP.

8.1.4. Pregnancy

Female subjects and male subjects with pregnant partners who becomes pregnant during the study must stop IMP and the Principal Investigator should report the pregnancy to Covance Safety (CRO/Rafael) on the applicable pregnancy report form. The subject must be discontinued from the trial medication immediately and the subject or the pregnant partner will be followed until the conclusion of the pregnancy with the outcome being reported as an update to the pregnancy form.

8.2. Classification of an Adverse Event

8.2.1. AE Severity Grade

Table 18 Adverse Event Severity Grading

Severity (Toxicity Grade)	Description
Grade 1	Mild: events require minimal or no treatment and do not interfere with the participant's daily activities.
Grade 2	Moderate: events result in a low level of inconvenience or concern with the therapeutic measures. Moderate events may cause some interference with functioning.
Grade 3	Severe: events interrupt a participant's usual daily activity and may require systemic drug therapy or other treatment.
Grade 4	Life threatening or disabling: patient at risk of death at the time of the event.
Grade 5	Death related to AE

8.2.2. Severity of Adverse Events

The Cancer Therapy Evaluation Program (CTEP) Active Version of the NCI Common Terminology Criteria for Adverse Events (CTCAE 4.0) will be utilized for Adverse Event (AE) reporting. The CTEP Active Version of the CTCAE is identified and located on the CTEP website at: http://ctep.cancer.gov/protocolDevelopment/electronic_applications/ctc.htm All appropriate treatment areas should have access to a copy of the CTEP Active Version of CTCAE. If a particular AE's severity/intensity is not specifically graded by the guidance document, the investigator will revert to general definitions of grade 1 through grade 5 and use his or her best medical judgement.

Evaluation of an Adverse Event (AE):

- **Definitely Related** – A clinical event follows a reasonable temporal sequence from the time of Investigational Product (devimistat) administration, cannot be reasonably explained by other factors such as the subjects medical condition, or concurrent medical condition, or concurrent medication(s) AND either occurs following active Investigational Product (devimistat) administration, improves on stopping the Investigational Product (devimistat), or reappears on re-exposure
- **Probably Related** – A clinical event follows a reasonable temporal sequence from the time

of Investigational Product (devimistat) administration. The toxicity cannot be reasonably explained by other factors such as the subjects clinical state or concurrent medical condition, or concurrent medication(s)

- **Possibly Related** – A clinical event follows a reasonable temporal sequence from the time of active Investigational Product (devimistat) administration but could also have been produced by other factors such as the subjects clinical state, or concurrent medical condition, or concurrent medication(s)
- **Unlikely Related** – A clinical event is doubtfully related to active Investigational Product (devimistat). The event was most likely related to other factors such as the subject's clinical state, or concurrent medical condition, or concurrent medication(s) or the temporal relationship to the administration and/or exposure suggests that a causal relationship is unlikely
- **Not Related** - The event is clearly due to causes other than the Investigational Product (devimistat)

List of adverse events (AEs) for devimistat:

Definitely Related to devimistat:

- Hyponatremia
- Hyperglycemia
- Lymphocyte Count Decrease

Probably related to devimistat:

- *Increased Creatinine
- *Vomiting
- *Nausea
- *Diarrhea

Asterisk () denotes expected Adverse Events.*

Possibly related to devimistat:

- Increased Alkaline phosphatase

- Anorexia
- ALT (SGPT)
- AST (SGOT)
- Bilirubin (hyperbilirubinemia)
- Calcium (hypercalcemia, hypocalcemia)
- Flushing
- Hemoglobin (anemia)
- Leukocytes
- Lymphopenia
- Neutrophils (neutropenia)
- Platelets (thrombocytopenia)
- Potassium

List of adverse events for FFX

Definitely related to FFX:

- Neutropenia
- Febrile neutropenia
- Thrombocytopenia
- Anemia
- Fatigue
- Vomiting
- Diarrhea
- Sensory neuropathy

Possibly related to FFX:

- Elevated level of alanine aminotransferase
- Thromboembolism

Tumor flare leading to biliary obstruction is also a possible side effect of treatment but will not disqualify patients from study participation. In the event that tumor flare occurs, patients may be treated with a stent.

8.2.3. Expectedness

AEs can be 'Unexpected' or 'Expected' for expedited reporting purposes only.

Covance will be responsible for determining whether an AE is expected or unexpected. An AE will be considered unexpected if the nature, severity, or frequency of the event is not consistent with the risk information present in the Investigator's brochure.

8.3. Time Period and Frequency for Event Assessment and Follow-Up

The occurrence of an AE or SAE may come to the attention of study personnel during study visits and interviews of a study participant presenting for medical care, or upon review by a study monitor. All AEs including local and systemic reactions not meeting the criteria for SAEs will be captured in the CRF. Information to be collected includes event description, time of onset, clinician's assessment of severity, relationship to study product (assessed only by those with the training and authority to make a diagnosis), and time of resolution/stabilization of the event. All AEs occurring while on study must be documented appropriately regardless of relationship, action taken with study drug (drug withdrawn, dose reduced), other treatment for AE (drug therapy, other procedure) and outcome of AE. All AEs will be followed to adequate resolution (return to baseline).

Any medical condition that is present at the time that the participant is screened will be considered as baseline and not reported as an AE. However, if the study participant's condition deteriorates at any time during the study, it will be recorded as an AE. UPs will be recorded in the data collection system throughout the study.

Changes in the severity of an AE will be documented to allow an assessment of the duration of the event at each level of severity to be performed. AEs characterized as intermittent require documentation of onset and duration of each episode. Disease progression will not be considered as an AE/SAE.

The PI will record all reportable events with start dates occurring any time after informed

consent is obtained until 7 (for non-serious AEs) or 30 days (for SAEs) after the last dose of the study drug. At each study visit, the investigator will inquire about the occurrence of AE/SAEs since the last visit. Events will be followed for outcome information until resolution or stabilization.

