5.3. End of Treatment

Subjects should return to the study site for an End of Treatment Visit within approximately 7 days after treatment discontinuation of all study medication (CPI 613[®] + mFFX or FFX) and prior to initiation of subsequent anticancer therapy. Adverse events and concomitant medications will be reviewed at this visit, and the following assessments should be completed:

- Physical Examinations
- Vital Signs
- ECOG Performance Status
- Weight/BSA
- Obtain CT scan (or MRI) if radiologic disease progression was not documented in the previous CT scan (or MRI) unless the latter one was performed within the last 14 days
- Blood sample collection for the following tests: Hematology, Blood Chemistry, and CA 19-9
- Collect AE and SAE
- Pregnancy test
- NCCN-FACT FHSI-18 Questionnaire

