5.3.1. Discontinuation of Treatment

The Investigator must protect the subject's welfare and may discontinue any study treatment at any time when this action appears to be in the subject's best interest. The reason for the subject's discontinuation must be recorded in the subject's electronic case report. Possible reasons for the discontinuation may include, but are not limited to, the following:

- Disease Progression defined as follow: disease progression documented by CT scan (or MRI) based on RECIST version 1.1 criteria, as determined in the protocol;
- Adverse Event;
- Any significant Protocol Violation as per protocol;
- Withdrawal of consent by an enrolled subject.

5.3.1.1 Patients requiring delay for more than 3 weeks because of toxicity.

- 5.3.1.2 Unacceptable toxicity from FFX or mFFX + devimistat (Grade 3 or more severity of toxicity).
- 5.3.1.3 The subject becomes pregnant (treatment should be discontinued immediately)
Intercurrent illness with a condition, injury, or disease unrelated to the intended disease for which the study is investigating, that renders continuing the treatment unsafe or regular follow-up impossible.
- 5.3.1.4 General or specific changes in the patient's condition that in the opinion of the treating physician renders the patient ineligible for further investigational treatment.
- 5.3.1.5 Recurrent grade 4 adverse events despite all appropriate dose reductions.
- 5.3.1.6 Non-compliance with investigational treatment, protocol-required evaluations or follow-up visits.
- 5.3.1.7 Other reasons as determined by the Investigator or Sponsor: A subject may have study treatment discontinued if, in the opinion of the Investigator or Sponsor, it is not in the subject's best interest to continue; Unambiguous clinical progression documented by the Investigator in the absence of radiological confirmation.

Subjects who discontinue all study medication for any reason should remain in the study for long-term follow up assessments unless they withdraw informed consent, die, or become lost to follow up. Long-term follow up evaluations will be performed accordingly as described in the protocol. In the event of study treatment discontinuation, the subject should be instructed to report to the site as early as possible after the decision to discontinue study treatment has been made. All End of Treatment procedures should be performed according to the protocol.

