6.1.5. Dosing and Administration

CPI-613[®] (devimistat) and modified FOLFIRINOX (Experimental Arm1: CPI-613[®] (devimistat) + mFFX):

Calculation of the Dose of CPI-613[®] (devimistat) and modified FOLFIRINOX for Each Patient:

The amount of devimistat and each of the drug constituents of modified FFX is based on the body surface area (BSA) of each patient. The BSA values will be calculated based on the height and body weight taken during screening and this BSA value is used throughout the study using a standard formula, such as Mosteller formula. If the subject's body weight changes by >10% from one visit to the next, the BSA should be recalculated and the dose adjusted. There is no maximum dose and patients' actual weight should be used for dose calculation.

The Timing of Dosing (CPI-613[®] (devimistat)):

In a 14-day's cycle (+/- 24 hours), devimistat is to be given on Day 1, prior to administration of mFFX. It is also given on Day 3, after completion of mFFX administration. On day 3, in the event that time will not permit devimistat administration following 5-FU infusion, devimistat may be administered concurrently with 5-FU via a double lumen port.

Administration (CPI-613[®] (devimistat)):

Devimistat must be administered intravenously, via a central venous catheter that is free flowing and free of air in the dead space of the IV catheter, to minimize vascular irritation, inflammation and acute toxicity of devimistat. Accidental co-administration of extra air in the dead space of IV catheters during administration of devimistat has demonstrated the potential to induce acute toxicity of devimistat according to animal studies. Also, accidental leakage of devimistat into the perivascular space during IV administration, which prolongs exposure of perivascular tissue to devimistat, can induce significant local inflammation according to animal studies. To avoid local reactions at and around the site of administration, devimistat must be administered via a central venous catheter.

Diluted devimistat **MUST** be administered as by **IV infusion** and not as bolus via a central venous catheter **at the rate of 4 mL/min** on Day 1 and Day 3 of each cycle via an infusion pump. This is to minimize potential acute toxicity of devimistat, according to animal studies. Devimistat infusion must be administered concurrently with D5W at the rate of 125mL/hour (2.08mL/min) via a central venous catheter.

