6.1.6. Dose Adjustments/Modifications/Delays

No dose modifications are allowed for devimistat in this study.

The dose of Folinic Acid is not modified for any toxicity but is omitted if fluorouracil is omitted. Once a dose of any of the drugs comprising FFX is decreased, re-escalation of the dose is not permitted. Patients are taken off the study if they develop the same Grade 4 toxicity despite dose reduction. The dose adjustment scheme for FFX is dependent on the type of toxicities, as described below.

Hematologic Toxicity

Once hematologic toxicity is observed in a patient, do not retreat the patient with mFFX or FFX until the absolute neutrophil count is $\geq 1.5 \times 10^9/L$ and the platelet count is $\geq 75 \times 10^9/L$. The dose modification schemes for FFX related to hematologic toxicity are shown in Table 9.

Primary prophylaxis with myeloid growth factor will be at the discretion of the treating physician and as per the ASCO guidelines. If the patient is not being treated with myeloid growth factor the initial modification for neutropenia should be the addition of a myeloid growth factor. If the patient is already on a myeloid growth factor, then dose adjustments are as outlined in Table 9.

Table 9 Dose Modifications for Hematological Toxicities on Day 1 of a Cycle. Cycles are Every Two Weeks.

Day 1	Delay the Start of a Treatment Cycle*	Doses Reduction		
		Irinotecan	Oxaliplatin	Fluorouracil (5-FU)
ANC <1.5x10 ⁹ /L	Withhold treatment until granulocytes ≥1.5x10 ⁹ /L.	1 st occurrence: Continue same dose	1 st occurrence: Continue same dose	1 st occurrence: Delete bolus 5-FU
		2 nd occurrence: Reduce to 80% of starting dose	2 nd occurrence: Continue same dose	
		3 rd occurrence: Reduce to 50% of starting dose	3 rd occurrence: Reduce to 80% of starting dose	
		4 th occurrence: Discontinue irinotecan	4 th occurrence: Continue on 80% of starting dose	
Platelets <75x10 ⁹ /L	Withhold treatment until platelets ≥75x10 ⁹ /L.	1 st occurrence: No dose reduction	1 st occurrence: No dose reduction	1 st occurrence: Delete bolus 5-FU
		2 nd occurrence: Reduce to 80% of starting dose	2 nd occurrence: Reduce to 80% of starting dose	
		3 rd occurrence: Reduce to 50% of starting dose	3 rd occurrence: Discontinue oxaliplatin	
		4 th occurrence: Discontinue irinotecan	4 th occurrence: Discontinue oxaliplatin	

Table 10 Dose Adjustments According to Non-Hematological Toxicities (Excluding Alopecia, Nausea and Vomiting).

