9.4.4. Safety Analyses

The assessment of safety will be based mainly on the frequency of adverse events based on the Common Terminology Criteria for Adverse Events (CTCAE version 4) grade. Adverse events will be coded according to MedDRA, current version. The safety outcomes will include the occurrence of at least one serious adverse event, of at least one grade 3/4 adverse event, and of at least one adverse event requiring the discontinuation of study treatment.

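### The 7-day limit on recording non-serious adverse events ends before the next dose is due and conflicts with other recording rules in the protocol, so late-onset events in patients who stop may be missed

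*Protocol*

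**What the plan says.** Protocol section 8.3 sets the recording period by the date an event starts. The sentence opens "The PI will record all reportable events with start dates occurring any time after informed" and continues "consent is obtained until 7 (for non-serious AEs) or 30 days (for SAEs) after the last dose of the study drug". The same section also states: "All AEs occurring while on study must be documented appropriately regardless of relationship". Section 8.4.1 makes the investigator responsible for documenting every adverse event during the study. It also requires clinically significant laboratory abnormalities, including those that lead to permanent discontinuation, to be entered on the CRF.

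On dosing, section 6.1.5 states: "In a 14-day's cycle (+/- 24 hours), devimistat is to be given on Day 1, prior to administration of mFFX". Devimistat is given again on Day 3, and in both arms the 5-FU infusion finishes on Day 3. Section 7.3.3 starts Cycle 2 on Day 15. Table 9 in section 6.1.6, titled "Dose Modifications for Hematological Toxicities on Day 1 of a Cycle", bases treatment decisions on the counts found that day.

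The End of Treatment visit (sections 5.3 and 7.3.4) takes place within about 7 days of stopping all study medication. Of that visit the protocol says: "Adverse events and concomitant medications will be reviewed at this visit".

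The safety outcomes in section 9.4.4 include the occurrence of at least one grade 3/4 event and of "at least one adverse event requiring the discontinuation of study treatment". SAP section 6.3.3 plans a table of patients with an event that led to a change in study medication, permanent discontinuation included.

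**The concern.** The 7-day limit for non-serious events ends before the visit at which the next cycle is given, held or abandoned. For a patient who resumes this does no harm, because the later dose becomes the last dose and earlier events fall inside the window. For a patient who does not resume, a non-serious event with late onset is past the limit. Whether the same event is recordable then depends on whether treatment ended, which is what the discontinuation outcome is meant to measure.

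The 30-day limit for serious events does not remove the problem, because a grade 3/4 event need not be serious. In the phase I trial (Appendix III), grade 3-4 neutropenia was seen in 5 of 18 patients and hypokalemia in 6 of 18 at the 500 mg/m² dose, while each is listed as an expected serious event in only 1 of 20. The denominators differ, but most of these events were evidently not classed as serious.

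Because the protocol also asks for all adverse events, some sites may stop at 7 days and others may not.

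**Working it through.** **Inputs.** Cycle length 14 days, with a 24-hour tolerance either way (6.1.5). Last dosing day of a cycle: Day 3 in both arms (Tables 7 and 8). Non-serious window: 7 days by start date (8.3). End of Treatment visit: within about 7 days of discontinuation (7.3.4).

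**Calendar.**
- Cycle 2 Day 1 = 1 + 14 = Day 15, which matches section 7.3.3.
- Last dose to next dose = 15 − 3 = 12 days.
- Non-serious window closes on Day 3 + 7 = Day 10.
- Uncovered = 12 − 7 = 5 days, that is, onset on days 8 to 12 after the last dose.

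**Range.**
- If each dose can move by a day, the interval is 12 − 2 = 10 to 12 + 2 = 14 days, which leaves 3 to 7 days uncovered.
- Section 7.3.3 starts Cycle 3 on Day 30. From Day 17 (Cycle 2 Day 3) that is 13 days, with 6 uncovered.
- Any delay after the due date adds to the uncovered stretch for a patient who never resumes.

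**Where the checks fall.** Section 7.2.1 schedules blood tests on Day 1 and on Day 7 or 8. The mid-cycle test is 4 to 5 days after the last dose, inside the window. The next one, on Day 15, is 12 days after it, outside. A cytopenia absent on Day 8, found on Day 15 and dated by detection starts after the limit.

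**End of Treatment visit.** For a stop decided on Day 15, the visit falls 12 to 12 + 7 = 19 days after the last dose, past the 7-day limit. It therefore reviews events that the limit leaves out.

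**Possible size, by assumption only.** The documents give no onset times. Take non-serious events that cause a stop at the next visit, all with onset within 12 days of the last dose.
- Uniform onset: share with onset after day 7 = 5/12 = 42%.
- Exponential onset with parameter m days, truncated at 12: share = (e^(−7/m) − e^(−12/m)) / (1 − e^(−12/m)). For m = 2, 3, 5 and 7 this is about 3%, 8%, 17% and 23%.

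The 3% to 42% range reflects the assumed pattern, and only at sites that apply the 7-day limit strictly.

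**The clock.** Section 8.3 refers to the study drug without defining it. Section 5.3 speaks of all study medication. Section 6.1.1 uses study drug for the product the sponsor ships, and FFX is not supplied. If it means devimistat, the control arm has no clock.

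**The case against.** Much of the case on the other side stands.

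- **The window runs on onset.** A reader might infer that any toxicity that stops a patient at the next visit is lost. It is not: an event that starts within 7 days and persists to Day 15 is inside the window, even if treatment never resumes. Serious events are covered to 30 days.
- **Delays of more than 3 weeks.** Section 5.3.1.1 lists "Patients requiring delay for more than 3 weeks because of toxicity" among the stopping reasons. Such a stop comes after Day 15 + 21 = Day 36, more than 33 days after the last dose, so a reader might infer that even the serious-event window has closed. That measures the date of the decision. Toxicity that caused the delay was present when the cycle was withheld, at about day 12, well inside 30 days.
- **Other rules capture some of these events.** Section 8.4.1 requires CRF entry of laboratory results that lead to discontinuation, which covers the Day 15 cytopenia. It does not cover symptomatic events.
- **The rules can all be met.** A reader might infer that the passages are impossible to follow together. The 7-day sentence does not forbid later entries, and a site that records everything breaks no rule. The SAP sets no end date for treatment-emergent events that would remove them.
- **There is a second source.** The reason for stopping is recorded (5.3.1) and tabulated (SAP 7.1). As planned, that table gives the primary reason and not the event's term or grade.
- **The grade 3/4 outcome is partly protected.** It counts patients with at least one event, so a patient with an earlier recorded grade 3/4 event is already counted.

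**Conclusion.** The point holds as an inconsistency in the recording rules that can cost data. The non-serious window closes 5 days before the next planned dose (3 to 7 with the visit tolerances). It conflicts with the broader instructions in 8.3 and 8.4.1 and with the End of Treatment review. Events exposed to loss are non-serious, start on about days 8 to 12 after the last dose or later in a delay, and occur in patients who never resume. Both the discontinuation outcome and the grade 3/4 outcome can lose events this way.

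An undercount is a risk, not an established fact. It depends on how sites read 8.3 and on onset patterns that the documents do not give.

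A reader might also infer a biased comparison, because the arms differ in oxaliplatin and irinotecan dose and in devimistat. The documents do not support that. The dosing calendar is the same in both arms, and nothing shows that late-onset stops differ between them. The undefined study drug is a separate reason to fix the wording, since the clock should be the same in both arms.

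**What to change.** Reconcile section 8.3 with sections 5.3, 7.3.4 and 8.4.1:

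1. Record all adverse events, serious or not, with onset up to 30 days after the last dose or up to the End of Treatment visit, whichever is later. The 30 days is the limit already used for serious events.
2. Record any adverse event given as the reason for stopping treatment, whatever its onset date.
3. Define last dose as the last dose of any study medication (devimistat or any FFX/mFFX component), so that both arms use the same clock.

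With a 30-day window, the uncovered days before the next planned dose fall from 5 to 0.

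The cost is a protocol wording change, an update to the eCRF guidance, more entries per patient and slightly higher reported counts. The End of Treatment visit alone cannot reach 30 days, so late non-serious events would be collected at contact around 30 days. The documents already imply such contact through the serious-event window, the 30-day pregnancy test in section 5.1.7 (women of child-bearing potential) and the 30-day follow-up column in SAP Appendix I. Protocol Tables 16 and 17 have no such column, so the amended text should name the contact.
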